10.3 Description of Statistical Methods

10.3.1 General Approach

This is a phase 1, randomized, double blind placebo controlled single center study to determine the effects of a postoperative single 0.6 mg/kg dose of ketamine on pain and recovery in patients having undergone robotic removal of endometriosis. Mood, anxiety, quality of life, physical function, and opioid use will also be measured.

Descriptive statistics will be used to summarize continuous variables with mean and standard deviation, or categorical variables with frequency and percentage. The normality of the distributions for continuous variables will be tested using Q-Q plots and Shapiro–Wilk tests. If the distribution is skewed, continuous variables will be summarized using median and the inter-quartile range. A two-sided p-value<0.05 will be considered statistically significant. All analyses will be conducted using R.

10.3.2 Analysis of the Primary Efficacy Endpoint(s)

The primary endpoint is postoperative pain assessed via the Visual Analogue Scale (VAS) at enrollment date, POD 1, POD 27, POD 55, and POD 83. The difference between the two arms (ketamine vs placebo) will be compared using Wilcoxon's rank sum test. To account for repeated measurements of postoperative pain scores on days 1, 27, 55, and 83, a mixed model repeated measures (MMRM) method

Version: 1.23

May 2, 2022 Page 24

will be used. This model will include the baseline pain scale, treatment, time, treatment by time interaction, and unbalanced baseline variables as relevant. Model based least square means will be obtained and reported at each time point.

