4.2 Study Endpoints

4.2.1 Primary Study Endpoints

The primary endpoint will be the assessment of pelvic pain using the Visual Analogue Scale (VAS) at enrollment date, POD 1, POD 27, POD 55, and POD 83. The VAS is a clinically relevant, valid, and reliable measure of pain.^{28–30} Post-operative participant self-reported scores will be used to determine the efficacy of the test drug in pain management.

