10.1 Statistical Hypotheses

The primary outcome will be the assessment of postoperative pain using the Visual Analogue Scale (VAS) between the ketamine and placebo arms at enrollment date, POD 1, POD 27, POD 55, and POD 83. We hypothesize that subjects who receive ketamine will have lower postoperative pain scores at all time points than those who receive placebo. Secondary outcomes include changes in opioid use between the ketamine and control arms, as well as changes in Endometriosis Health Profile-30, General Anxiety Disorder-7 (GAD-7), and Montgomery-Asberg Depression Rating Scales (MADRS). We hypothesize that subjects who receive ketamine will have decreased opioid use, as well as lower scores on the mood and quality of life scales above than those who receive placebo.

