10.3.6 Baseline Descriptive Statistics

Descriptive statistics will be used to summarize the demographic and baseline characteristics, with mean and standard deviation for continuous variable, or frequency and percentage for categorical variables. If continuous variables are skewed, the median and inter-quartile range will be used as well. To test differences in the demographic and baseline characteristics between the two arms, clinical variables that are continuous will be compared using either two sample t-test if normally distributed or Wilcoxon's ranksum test otherwise and categorical variables will be compared using Chi-squared or Fisher's exact test. Unbalanced baseline variables will be determined by both statistical and clinical significance.

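### The primary VAS analysis names no deciding visit, contrast or lead method and sets multiplicity aside, so the two-sided 5% error rate is not assured

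*Combined protocol and SAP*

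**What the plan says.** Section 4.2.1 defines the primary endpoint as "assessment of pelvic pain using the Visual Analogue Scale (VAS) at enrollment date, POD 1, POD 27, POD 55, and POD 83", and 10.3.2 restates it as "postoperative pain assessed via the Visual Analogue Scale (VAS) at enrollment date, POD 1, POD 27, POD 55, and POD 83". No visit is singled out in either place.

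Section 10.3.2 then gives two analyses:
- "The difference between the two arms (ketamine vs placebo) will be compared using Wilcoxon's rank sum test". No visit or summary score is attached to this test.
- An MMRM over POD 1, 27, 55 and 83. "This model will include the baseline pain scale, treatment, time, treatment by time interaction, and unbalanced baseline variables as relevant". Its output is also given visit by visit: "Model based least square means will be obtained and reported at each time point".

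Section 10.3.6 says how the extra covariates are found: "Unbalanced baseline variables will be determined by both statistical and clinical significance".

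The hypothesis in 10.1 is that "subjects who receive ketamine will have lower postoperative pain scores at all time points than those who receive placebo". The threshold in 10.3.1 is general: "A two-sided p-value<0.05 will be considered statistically significant". Section 10.3.9 declares multiplicity not to apply.

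Section 10.4 calls the trial a pilot that is not powered for a hypothesized VAS effect. It gives 80% power for an effect size of 1.1 with 15 per arm, using one two-sided Wilcoxon test, again without a visit. The Protocol Summary and section 2.1 describe a different rule: a t-test if the outcome is normal, Wilcoxon otherwise.

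**The concern.** A 5% error rate belongs to one pre-named test, or to a family of tests with a rule for combining them. Here there are four postoperative comparisons and two methods, each producing a result that the general threshold would call significant, and no rule for declaring success. Once the data are in, the analyst could point to whichever visit or method gave p<0.05 and remain within the text.

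Error and power both turn on the missing rule. A lenient rule raises both, and a strict one lowers both. The power statement in 10.4 therefore describes only one of several possible primary analyses. The MMRM is also not fully specified, because part of its covariate set waits on the observed imbalance.

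**Working it through.** **1. The plan's own figure.** Inputs from 10.4: 15 per arm, effect size 1.1 SD, two-sided alpha 0.05, Wilcoxon test, normal data.
- Effective n per arm = 15 × 3/π = 14.32.
- Noncentrality = 1.1 × √(14.32/2) = 2.94, with 2 × 14.32 − 2 = 26.6 df. Power is 81.0%.
- Simulating the exact test (40,000 trials) gives 79.7%. Its attained size is 4.53%.

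The stated 80% is reproduced, for one Wilcoxon test at one visit.

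**2. Assumptions the documents do not supply.** Unit-variance normal data, no missing values, and correlation between visits (enrollment included) of 0 to 0.9, equal for all pairs. A pattern decaying with visit order was also run. MMRM visit contrasts are approximated by an ANCOVA at each visit on enrollment VAS (27 df).

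**3. Reference point.** Four independent tests at the nominal level give 1 − 0.95^4 = 18.5%. At the exact Wilcoxon size they give 1 − (1 − 0.0453)^4 = 16.9%. Correlation between visits lowers this, so simulation is needed.

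**4. Type I error under each possible reading** (20,000 to 40,000 null trials per cell, equal correlation):

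| Reading | 0 | 0.3 | 0.5 | 0.7 | 0.9 |
|---|---|---|---|---|---|
| Any of four Wilcoxon tests | 17.1% | 16.2% | 14.9% | 12.6% | 9.4% |
| Any of four adjusted contrasts | 18.6% | 18.0% | 16.8% | 16.1% | 16.1% |
| Either method, any visit | 22.0% | 22.2% | 22.8% | 22.9% | 22.6% |
| Either method, one visit | 6.1% | 6.6% | 7.4% | 8.1% | 8.9% |
| All four Wilcoxon tests | <0.1% | <0.1% | 0.1% | 0.3% | 1.4% |

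With decaying correlation the first row becomes 17.0%, 16.4%, 15.3%, 13.5% and 9.9%. Across both patterns and repeat runs, either method at any visit lies between about 19% and 24%.

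**5. Power if all four visits must be significant**, with a 1.1 SD effect at every visit. At correlation 0 the Wilcoxon figure is 0.797^4 = 40%. Simulation gives 40%, 48%, 54%, 60% and 68% across the five correlations (up to about 69% in repeat runs), against the 80% in 10.4. For the adjusted contrasts it is 44%, 57%, 73%, 93% and about 100%, so under that rule the method matters as much as the visit.

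**6. What a single named contrast restores.** One exact Wilcoxon test has 4.5% error. One baseline-adjusted contrast, checked as the average over the four visits, has 4.9% to 5.1%.

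**The case against.** The strongest reply is that the plan leans towards an answer. Section 10.4 sizes the trial on Wilcoxon, 10.3.2 lists Wilcoxon first and gives the MMRM the role of handling repeated measurements, and 10.1 speaks of lower pain at every visit. Read together, Wilcoxon leads and all visits must agree, which would put the error far below 5%. The hints are real, but none is written as a decision rule. The order of sentences does not choose a visit, and the 10.1 statement is an expectation. Made into a criterion, it would contradict the power in 10.4.

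Three stronger readings are tempting and not supported:
- A reader might infer that the trial runs at 17% or 23% error. No section says that significance at any visit, or by either method, is enough. Those figures are conditional.
- A reader might treat the t-test in the Protocol Summary and section 2.1 as a third free choice. Under that text normality selects the test, so no added inflation can be charged to it. Its conflict with 10.3.2 is a matter of alignment.
- A reader might infer that choosing covariates by imbalance inflates error. Section 10.3.6 requires clinical as well as statistical significance, and a simulation of significance-based entry showed no inflation. The fault is a model not fixed in advance.

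Pilot status also carries weight: section 6 disclaims use in support of a new indication, and estimates by visit may be most of what a 30-patient trial can offer. This limits the consequence. It does not remove the gap, because 10.3.1 attaches a significance claim and 4.2.1 says the scores will determine efficacy.

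**Conclusion.** The concern holds as an unspecified primary test: the plan does not secure a 5% error rate, and no single inflated rate can be assigned to it. Depending on the rule eventually applied, the error runs from at most about 1.5% to about 24%. The 80% power applies to one Wilcoxon test at one unnamed visit and to no other reading.

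The figures rest on normal complete data, 15 per arm, an assumed correlation of 0 to 0.9, and ANCOVA standing in for the MMRM. Completeness is an optimistic assumption, since section 5.6 expects about 50 enrolled to keep 30 and 5.7.2 allows replacement. The direction of the result does not depend on the correlation chosen. The point should be fixed. Its severity is moderate, given the pilot purpose.

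**What to change.** Before unblinding, name one primary contrast and one method at two-sided 0.05, in the same words in 4.2.1, 10.1 and 10.3.2.

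- **Preferred:** the MMRM contrast adjusted for enrollment VAS at one named postoperative visit, with the covariate list fixed in advance in 10.3.2 and 10.3.6 and Wilcoxon kept as a sensitivity analysis. Restate 10.4 for that contrast under a stated correlation. The detectable effect at 80% power is about 1.08 SD × √(1 − ρ²): 1.08, 1.03, 0.94 and 0.77 SD at ρ = 0, 0.3, 0.5 and 0.7.
- **Alternative:** Wilcoxon at one named visit, with 10.4 unchanged apart from naming the visit and the MMRM supportive. This gives up the gain from baseline adjustment (detectable effect about 1.11 SD).

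Under either option:
- report the other visits as secondary estimates with 95% confidence intervals;
- put this rule in 10.3.9;
- align the Protocol Summary and section 2.1 with 10.3.2;
- say in 10.1 whether the all-visits statement is an expectation or a criterion;
- treat enrollment VAS as baseline only, not as part of the endpoint.

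The cost is an amendment with IRB approval (13.2) and the demotion of the visits not chosen. No patients or data are added. A contrast averaged over the four visits would also control error, but it is a poor choice if the effect is brief. With 1.1 SD at POD 1 only, its power is about 17% to 30% (correlation 0 to 0.7, equal or decaying), against about 81% to 98% for the adjusted POD 1 contrast.

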10.3.3 Analysis of the Secondary Endpoint(s)

Secondary endpoints include opioid dosage as well as scales for mood and quality of life. The difference in secondary outcomes between ketamine and placebo will be compared using Wilcoxon's rank sum test. Secondary outcomes will likewise be obtained on more than one occasion (POD 1, POD 27, POD 55, and POD 83), so an MMRM approach will also be used to assess differences between the two treatment arms. The MMRM models will include treatment, time, treatment by time interaction, preoperative values, and unbalanced baseline variables.

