10.4 Sample Size

This is a pilot study with limited resources so that it is not powered to detect a hypothesized effect size for VAS. We expect to randomize 15 participants to each arm. With 15 subjects per arm, we have 80% power to test an effect size of 1.1 with a significance level (alpha) of 0.05 using a two-sided Wilcoxon's rank-sum test assuming data are generated from normal distributions.

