10.4.1 Enrollment/Randomization/Masking Procedures

The subjects will be randomized in a 1:1 ratio. The treatment subjects will receive 0.6 mg/kg of the study drug, and the control subjects will receive an equal volume of saline. Participants will be randomized with random size permuted blocks, blinded with respect to treatment assignments. [name] (the PI) will generate the randomization list.

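### The arm comparison named first for the primary and secondary endpoints, and the only one with a stated power, is a Wilcoxon test with no baseline term, so precision is lost wherever its p-value is relied on

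*Combined protocol and SAP*

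**What the plan says.** Section 4.2.1 defines the primary endpoint as "the assessment of pelvic pain using the Visual Analogue Scale (VAS) at enrollment date, POD 1, POD 27, POD 55, and POD 83". Section 4.2.2 and the schedule of events show that EHP-30, GAD-7, MADRS and opioid use are also recorded at enrollment.

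Section 10.3.2 opens the primary analysis with: "The difference between the two arms (ketamine vs placebo) will be compared using Wilcoxon's rank sum test". It names no covariate and no time point, and does not say whether scores or changes are ranked. It then plans an MMRM over POD 1, 27, 55 and 83 that includes baseline pain and reports least square means at each visit.

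Section 10.3.3 has the same pair of analyses: "The difference in secondary outcomes between ketamine and placebo will be compared using Wilcoxon's rank sum test", followed by an MMRM that includes the preoperative value.

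Section 10.4 attaches power to the rank-sum test only: "we have 80% power to test an effect size of 1.1 with a significance level (alpha) of 0.05 using a two-sided Wilcoxon's rank-sum test". The Protocol Summary and section 2.1 name only a t-test or a Wilcoxon test and do not mention the MMRM.

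No section says which of the two analyses decides. Section 10.3.1 applies a two-sided 0.05 level throughout, and section 10.3.9 treats multiplicity as not applicable.

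**The concern.** With 15 women per arm and no stratification factor in section 10.4.1, preoperative pain can differ between arms by chance. A two-sample rank-sum test on follow-up scores carries that difference into the result and leaves stable between-woman differences in the error. The plan treats baseline as relevant in one analysis of each endpoint and omits it from the other, so the two can disagree for that reason alone. If the Wilcoxon p-value is then taken as the answer, the trial may miss an effect that its own baseline-adjusted model shows. The power statement also describes only the less precise of the two analyses.

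**Working it through.** **Inputs from the plan.** n = 15 per arm, 1:1 allocation, standardized effect d = 1.1, two-sided alpha 0.05, normal data, stated power 80% (sections 10.4 and 10.4.1).

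**Assumption.** The documents give no correlation (rho) between baseline and follow-up score. Values from 0 to 0.7 are shown.

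**Step 1: reproduce the stated figure.** Simulation of the two-sided rank-sum test with its exact critical value (100,000 trials per setting) gives 79.5%. The large-sample version gives 80.9%. A noncentral t with n multiplied by 3/pi gives 81.0%. The stated 80% holds.

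**Step 2: size of a chance imbalance.** The standard error of the baseline difference between arms is sqrt(2/15) = 0.37 SD. At rho = 0.5 a typical imbalance moves the unadjusted follow-up difference by about 0.5 x 0.37 = 0.18 SD.

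**Step 3: what adjustment removes.** The error variance falls by the factor 1 - rho^2, so the effective standardized effect becomes d / sqrt(1 - rho^2):
- rho = 0.2: 1.1 / sqrt(0.96) = 1.12
- rho = 0.3: 1.1 / sqrt(0.91) = 1.15
- rho = 0.5: 1.1 / sqrt(0.75) = 1.27

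Read the other way, at rho = 0.5 the effect detectable at roughly the same power falls from 1.1 to about 1.1 x sqrt(0.75) = 0.95.

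**Step 4: simulated power at d = 1.1 (%).**

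| rho | Wilcoxon | t-test | Rank ANCOVA | Linear ANCOVA |
|---|---|---|---|---|
| 0 | 79.5 | 82.8 | 79.6 | 81.2 |
| 0.2 | 79.7 | 82.9 | 81.1 | 82.9 |
| 0.3 | 79.6 | 82.9 | 82.8 | 84.9 |
| 0.4 | 79.7 | 82.9 | 85.2 | 87.5 |
| 0.5 | 79.5 | 82.8 | 88.3 | 90.8 |
| 0.6 | 79.4 | 82.8 | 92.1 | 94.4 |
| 0.7 | 79.4 | 82.6 | 96.1 | 97.8 |

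Linear ANCOVA stands in for a single-visit MMRM contrast with complete data. The MMRM itself was not simulated.

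**Step 5: separate the two sources of gain.** From unrounded values at rho = 0.5:
- Baseline adjustment alone is worth 8.8 points on ranks (79.5 to 88.3) or 8.0 points in normal theory (82.8 to 90.8).
- Wilcoxon to linear ANCOVA is 11.2 points. Leaving ranks under normal data accounts for 2.4 of these (88.3 to 90.8) or 3.2 (79.5 to 82.8), depending on the order in which the steps are taken.

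At rho = 0.2 and 0.3 the rank-based gain is only 1.4 and 3.2 points.

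**Step 6: type I error.** A separate run of 8,000 trials per setting at rho = 0.5 gives 0.044 for Wilcoxon, 0.048 for Quade rank ANCOVA and 0.049 for linear ANCOVA. The gain is not bought with false positives.

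**Step 7: dependence on d.** At rho = 0.5 the gains over Wilcoxon (rank / linear) are 11.1 / 14.8 points at d = 0.8 and 6.4 / 8.3 points at d = 0.5.

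**The case against.** The strongest reply is that the plan already adjusts for baseline. The MMRM in sections 10.3.2 and 10.3.3 includes the baseline value and reports least square means at every visit. This stands. A reader might infer that the plan ignores baseline, or that the trial as a whole forfeits 8 to 11 points of power. The documents support neither: the loss is confined to the Wilcoxon result and matters only if that result is relied on, which the plan leaves open.

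A reader might also infer that the sample size was derived from this test. Section 10.4 says otherwise: "This is a pilot study with limited resources so that it is not powered to detect a hypothesized effect size for VAS". The 1.1 figure describes a detectable effect at an n set by resources.

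The gain rests on an unstated correlation. There are reasons to expect a lower one at POD 1. Baseline is chronic pain restricted to moderate or severe, consent may precede surgery by up to two months, and an operation intervenes. This stands, and the gain could be as small as 1 to 3 points for the rank test.

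The Protocol Summary would use a t-test for normal data. Against that comparator the rank-based fix gains about 88.3 - 82.8 = 5.5 points at rho = 0.5.

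The text may intend ranks of change scores; section 10.1 speaks of changes for the secondary outcomes. That would deal with baseline imbalance but not with power. The variance of a change is 2(1 - rho) times the single-score variance, so it is equal at rho = 0.5 and larger below it.

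Finally, baseline score is not the only adjustment the plan allows, since both MMRMs may also take in unbalanced baseline variables. None of these replies gives the Wilcoxon comparison a baseline term or makes the adjusted model decisive.

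**Conclusion.** The point holds as an inexpensive improvement to an open choice, not as an error in the power calculation, which reproduces. The only comparison with a stated power leaves out a covariate that the enrollment visit already collects. Where its p-value is relied on at d = 1.1 and 15 per arm, power is about 79 to 80%. A baseline-adjusted rank test would give about 81%, 82 to 83% and 88% at rho = 0.2, 0.3 and 0.5, and a linear adjusted analysis about 83%, 85% and 91%. These figures assume bivariate normal scores, complete data and a correlation that the documents do not give. At rho = 0 the rank-based adjustment costs essentially nothing (79.6% against 79.5%), so the direction does not depend on the assumed value, although the size does.

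**What to change.** In sections 10.3.2 and 10.3.3, make the deciding arm comparison baseline-adjusted by one of two routes:

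- Use the treatment contrast from the MMRM already planned as the deciding analysis and keep Wilcoxon as a sensitivity analysis. The contrast must be named, because section 10.3.2 gives no deciding time point.
- Replace Wilcoxon with Quade rank ANCOVA: rank the follow-up and enrollment scores, regress the first set of ranks on the second, and compare the residuals between arms.

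In section 10.4, label the 1.1 and 80% figures as the unadjusted, conservative case and add adjusted power at stated correlations, for example 0.3 and 0.5.

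The cost is SAP wording and a few lines of R, with no new patients, visits or data. The rank version is less familiar, gives no estimate on the VAS scale (the MMRM does), and needs a recorded baseline score, which Visit 1 already requires.

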10.3.3 Analysis of the Secondary Endpoint(s)

Secondary endpoints include opioid dosage as well as scales for mood and quality of life. The difference in secondary outcomes between ketamine and placebo will be compared using Wilcoxon's rank sum test. Secondary outcomes will likewise be obtained on more than one occasion (POD 1, POD 27, POD 55, and POD 83), so an MMRM approach will also be used to assess differences between the two treatment arms. The MMRM models will include treatment, time, treatment by time interaction, preoperative values, and unbalanced baseline variables.

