4.2.2 Secondary Study Endpoints

The secondary endpoints will examine short- and long-term recovery, opioid use, side effects and adverse events.

- Endometriosis Health Profile-30 (EHP-30): A Health-Related Quality of Life (HRQoL) patient self-report tool used to measure the wide range of effects that endometriosis can have on patients' lives, including work, relationship with child/children, sexual relationship, feelings about medical profession, feelings about treatment, and feelings about infertility. This report will be completed on the enrollment date, POD 1, POD 27, POD 55, POD 83. The EHP-30 will be used to measure the quality-of-life component of short- and long-term recovery.
- 2. General Anxiety Disorder-7 (GAD-7): A Self-administered 7 item instrument that uses some of the DSM-V criteria for General Anxiety Disorder to identify probable cases of GAD along with measuring anxiety symptom severity. The GAD-7 assessments will be completed on the enrollment date, POD 1, POD 27, POD 55 and POD 83. The GAD-7 will be used to measure the anxiolytic effects of the test drug.
- 3. Montgomery-Asberg Depression Rating Scale (MADRS): A 10 item questionnaire often used by psychiatrists to measure the severity of depressive episodes in patients with mood disorders. MADRS assessments will be completed on the enrollment date, POD 1, POD 27, POD 55 and POD 83. The MADRS will be used to measure the antidepressant effects of the test drug.
- 4. Douleur Neuropathique 4 Questions (DN-4): This 10 item questionarre identifies neuropathic pain, which ketamine has been shown to address. This will allow for subgroup analyses that can shed light on best practice for these patients. The DN-4 will be completed at baseline by the study physician.
- Opioid use: The opioid use and dosage assessment will be assessed through medical records and subject reports. Assessment of opiate use will be used to determine the opiate-sparing effects of the study drug. Opioid use and dosage assessments will be completed on the enrollment date, POD 0, POD 1, POD 27, POD 55, and POD 83.
- 6. Assessment of Side Effects: A questionnaire will assess any potential side effects of the intervention at POD 0, POD 1, and POD 27.

May 2, 2022 Version: 1.23

, 2022 Page 10

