10.3.9 Multiple Comparison/Multiplicity

Not applicable to our study.

10.3.10 **Exploratory Analyses**

All analyses are specified as above; there are not planned exploratory analyses.

May 2, 2022 Version: 1.23

Page 25

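### Four secondary efficacy endpoints are tested at an unadjusted two-sided 5%, with no deciding visit or method and no exploratory label, so the chance of a false significant result is raised on every reading

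*Combined protocol and SAP*

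**What the plan says.** All references are to the combined protocol and SAP.

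- **Endpoints.** Section 10.1 begins its list of secondary outcomes thus: "Secondary outcomes include changes in opioid use between the ketamine and control arms, as well as changes in Endometriosis Health Profile-30". GAD-7 and MADRS complete it. The same section gives a direction: "We hypothesize that subjects who receive ketamine will have decreased opioid use, as well as lower scores on the mood and quality of life scales".
- **Role.** Section 4.2.2 says of opioid use: "Assessment of opiate use will be used to determine the opiate-sparing effects of the study drug". It says GAD-7 and MADRS measure anxiolytic and antidepressant effects.
- **Tests.** Section 10.3.3: "The difference in secondary outcomes between ketamine and placebo will be compared using Wilcoxon's rank sum test". It then applies an MMRM with treatment, time and their interaction, because the outcomes are collected at POD 1, 27, 55 and 83. It names no single visit, no summary contrast and no lead method.
- **Threshold.** Section 10.3.1: "A two-sided p-value<0.05 will be considered statistically significant". The sentence is not limited to the primary analysis.
- **Multiplicity.** The whole of section 10.3.9 reads "Not applicable to our study".
- **Exploratory analyses.** Section 10.3.10: "All analyses are specified as above; there are not planned exploratory analyses".
- **Study-level context.** Section 10.4 describes the trial as a pilot, not powered for a hypothesized VAS effect. The Protocol Summary words the objective as exploring an effect on pain and recovery.

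**The concern.** The secondary endpoints carry stated hypotheses, a significance rule and two tests each. They have no testing order, no division of alpha and no dependence on the VAS result. With several visits and two methods open, the analyst can also choose, after seeing the data, which p-value stands for an endpoint.

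If ketamine had no effect on any of these outcomes, the plan could still yield an opioid-sparing, antidepressant, anxiolytic or quality-of-life result that it permits to be called statistically significant. That could happen beside a negative VAS comparison, and nothing in the plan would tell a reader how much weight to give it.

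**Working it through.** **Inputs from the documents.** Two-sided alpha 0.05, undivided (10.3.1). Four endpoints (10.1). Four postoperative visits and two methods (10.3.3). 15 per arm, 1:1 (10.4, 10.4.1). DN-4 is not counted because it is collected only at baseline (4.2.2). Side effects and adverse events are not counted because they are summarized descriptively (10.3.4).

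**Inputs assumed.** The documents give no correlations between endpoints or between visits, so a range from 0 to 0.8 is used.

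**The plan's own figure.** Section 10.4 gives 80% power for effect size 1.1 with 15 per arm, two-sided 0.05, Wilcoxon rank-sum, normal data. Simulating the exact test (40,000 runs) gives 79.7%. The figure is reproduced and is not in dispute.

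**Independent tests.** The chance of at least one false positive in m independent tests is 1 - (1 - 0.05)^m.

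- m = 4: 1 - 0.95^4 = 0.185.
- m = 16 (4 endpoints x 4 visits): 1 - 0.95^16 = 0.560. Expected false positives: 16 x 0.05 = 0.8.
- m = 32 would give 0.806, but this is not usable: both methods analyse the same data, so their p-values are far from independent.

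**Equally correlated normal test statistics**, critical value 1.96, 400,000 draws:

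| Correlation | 0 | 0.2 | 0.5 | 0.8 |
|---|---|---|---|---|
| 4 tests | 18.6% | 18.1% | 15.5% | 11.4% |
| 16 tests | 56.0% | 51.7% | 37.5% | 20.8% |

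**Simulated trials**, 15 per arm, no true effect, four endpoints at baseline and four visits, complete normal data. A baseline-adjusted linear model stands in for the MMRM contrasts. Endpoint correlations run from 0 to 0.7 and visit correlations from 0.3 to 0.7; 8,000 runs per setting.

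- One baseline-adjusted contrast per endpoint, averaged over visits: 13-19%.
- The same averaged contrast by both methods, either counting: 18-30%.
- One method at all four visits: 31-51% by Wilcoxon, 40-55% by the adjusted model.
- Either method at any visit: 51-66%. With both correlations at 0.8 it falls to about 46-48%.

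**Combined ranges.**

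| Reading of 10.3.3 | Chance of at least one false positive |
|---|---|
| One test per endpoint | about 11-19% |
| One method, all four visits | about 21-56% |
| Either method, any visit | about 46-66% |

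**The Holm alternative.** The first step across four endpoints is 0.05/4 = 0.0125. Testing all four at that level gives 1 - (1 - 0.0125)^4 = 0.049 if independent, and simulation gives about 3-5%. Exact Wilcoxon power at effect size 1.1 falls from about 80% to about 59% at that step.

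**The case against.** The strongest reply is that this is a 30-patient Phase I pilot whose summary objective is to explore. Every section labels these outcomes secondary, no decision rule depends on them, and section 6 disclaims any intent to support a new indication. Much of this stands. It applies to the whole study, including the secondary endpoints, and it limits what is at stake. It does not override section 10.3.1, which attaches statistical significance to any p below 0.05 without exempting the secondaries.

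Three stronger readings are tempting, and the documents do not support them.

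- **That a false positive is likely.** Section 10.3.3 does not state that each visit is tested. Reporting least-squares means at each time point is specified only for the primary, in 10.3.2. Testing at each visit is an inference from the four listed visits, the interaction term and the absence of a chosen contrast. With one contrast per endpoint the rate is raised, but a false positive is far from likely.
- **That section 10.3.10 declares the secondaries confirmatory.** Beside the parallel sentence on subgroups in 10.3.8, it reads most naturally as saying that nothing further is planned. The gap is a missing label, not a confirmatory claim.
- **That the plan puts secondary results on the same footing as the primary.** No text says so. The two share a threshold; they do not share a rank.

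It may also be said that secondary endpoints need no adjustment. That is reasonable when they are labelled supportive or exploratory, and that label is what is missing.

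**Conclusion.** The point holds as a gap in labelling and error control for the secondary efficacy family. If ketamine affects none of the four endpoints, the chance of at least one result the plan would call significant exceeds 5% on every reading, from roughly one in nine at the lowest to roughly two in three at the highest. It is above one half over most of the range for either method at any visit, and only at the upper end for one method at every visit.

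These figures rest on assumed correlations, complete normal data, no true effect on any of the four endpoints and, for the two larger readings, inferred testing at each visit. They could be somewhat higher: EHP-30 covers several areas with no score named for testing, and opioid use is also assessed on POD 0. The pilot status makes this a cheap improvement rather than a flaw in the design.

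**What to change.** **Preferred change.**

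- Replace the text of 10.3.9 with: *Secondary efficacy endpoints are exploratory. They will be reported as treatment differences with 95% confidence intervals and nominal p-values, without multiplicity adjustment; no secondary result will be described as statistically significant or as establishing an effect.*
- In 10.3.1, state that the p<0.05 rule does not apply to the secondary efficacy endpoints. Leave it unchanged for the primary analysis and for the baseline comparisons in 10.3.6, where statistical significance helps decide which unbalanced variables enter the models.
- Reword 10.3.10 to say that no analyses beyond those specified are planned, so that it does not contradict the new label.
- Soften to *explore* the wording for opioid use, GAD-7 and MADRS in 4.2.2 and the secondary hypotheses in 10.1.

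Cost: a few sentences, with no added patients, visits or data and no change to any estimate or p-value. The downside is that a nominal p below 0.05 on a secondary endpoint can no longer be called significant.

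**Only if the sponsor wants a secondary claim.** Name one MMRM contrast per endpoint, the treatment difference averaged over the postoperative visits, and apply Holm across the four. This holds the family-wise rate at or below 5%. The cost is the loss of power shown above, to about 59% in Wilcoxon terms at the first step, which is why relabelling comes first.
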